## Summary

About 12,000 patients receive opioid agonist treatment in Ukraine, 83% of them are HCV-infected. Considering the rapidly increasing availability of DAA medications in Ukraine, this group can be efficiently covered with treatment using a simplified integrated HCV care model. The goal of the proposed project is to adapt and evaluate the effectiveness of a simplified HCV care and treatment model (SHIM) integrated into OAT clinics in Ukraine, using hybrid type 2 implementation science approach. SHIM implementation will be strengthened by Project ECHO (Extension for Community Healthcare Outcomes), a collaborative telehealth learning intervention, supporting and empowering clinicians to develop knowledge and self-efficacy about HCV care, which has not traditionally been integral to their scope of practice. As an implementation study, our project will generate much needed process data and clinical evidence for rapid scale-up of integrated HCV treatment in Ukraine and other countries of the region.

The Stage 1 aims are:

- 1) To develop SHIM and demonstrate its feasibility. We will develop the SHIM manual, train clinicians and conduct a pilot test with 20 OAT patients with HCV infection at an OAT clinic.
- 2) Using a multi-level implementation science framework, to examine the client, clinician and organizational factors that contribute to SHIM adoption and clinical outcomes.

If the pilot demonstrates feasibility and continuation is approved, the Stage 2 aim is:

- 3) To evaluate the effectiveness of SHIM in improving the HCV treatment cascade outcomes using a cluster-randomized three-arm trial design in 480 HCV-infected patients at 12 OAT clinics (4 clinics per arm) randomized to standard of care (N=160) versus SHIM with (N=160) or without (N=160) ECHO facilitation.

The primary outcomes of both pilot and main study phases are based on the HCV treatment cascade: (a) Completing the pretreatment evaluation; (b) Initiating and completing the full DAA course; (c) Achieving SVR12. Secondary outcomes will include treatment motivation, adherence, quality of life, treatment satisfaction. Although not sufficiently powered, we will measure re-infection rates among those achieving SVR.

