#### (5) posttreatment monitoring

HCV RNA PCR to confirm SVR will be performed 12 weeks following completion of therapy. If SVR is not achieved, the patient will be referred to a specialist for re-treatment. Annual HCV RNA testing will be recommended to evaluate for re-infection and liver function tests to monitor other liver conditions.

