### 3.2 Provision of DAA medications and laboratory tests

To enable on-site medication prescription and dispensing, we will work with the MoH through an established working group to re-route the required number of treatment courses procured by the MoH or regional programs to the OAT clinics.

Due to the centralized procurement (see Rationale), all regions have approximately same ratio of available formulations (with SOF+DAC comprising about 65% in the 2019 procurement). We will ensure that OAT clinics have at least one pan-genotypic regimen available (SOF+DAC or SOF/VEL). **Given the implementation science premise of this proposal, we will not control which regimens are prescribed by physicians.** Available pangenotypic DAA regimens are expected to have comparable effectiveness in our study population [16, 23]. Given that, and assuming even prevalence of genotypes and complicating conditions (e.g. cirrhosis) across the regions, we may safely assume that overall treatment effectiveness will not differ a priori, and the observed differences will result from the study interventions.

Medications will be provided to patients at no cost.

Currently, the diagnostic tests for HCV are provided at a wide range of public and private clinics and laboratories, however these assessments have to be paid for by patients. The average total cost for pre-treatment assessment is about \$100, including the complete blood count, metabolic panel, hepatic function panel, fibrosis staging, INR, but not including elastography. Given the implementation science nature of the proposed research, focusing on real-life outcomes, the costs of laboratory testing will NOT be covered by the project.

For those participants who complete HCV RNA PCR to confirm SVR, HCV RNA PCR for re-infection assessment (12 month after treatment completion) will be recommended. Cost of re-infection assessment will be reimbursed by the project.

### 3.3 Research methods for Aim 1

1) To develop SHIM and demonstrate its feasibility. We will finalize SHIM, train the clinicians and conduct a pilot-test in 10 OAT patients with HCV infection.

We will establish a technical working group on viral hepatitis elimination to finalize SHIM and oversee the study progress. The group will review the latest consensus documents [24], guidelines

(WHO, EASL, AASLD), and the National Standard [22] and produce a localized manual for simplified HCV integrated management model in non-specialty health care institutions.

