implementation and effectiveness of SHIM and ECHO implementation. Analyzing these trends will enable us to address important questions as: “How does organizational readiness to change influence uptake of the HCV care by the staff?” “Are certain subgroups of patients (e.g., younger vs. older) more likely to initiate HCV treatment?” Do changes in stigma (individual, healthcare setting) impact DAA retention or achievement of treatment goals. “Does the doctor/patient relationship influence the HCV care continuum?” “Does OAT patient caseload influence the coverage of SHIM?” Since the study data collection period is 18 months, temporal trends for measures will also be quantitatively described by providing parameters of best fitting parametric models (linear, quadratic/polynomial, exponential) to analyze such questions as: “Do increases in provider confidence lead to greater improvement in HCV cascade indicators?”

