### 3.5.5 Secondary Endpoints

Secondary outcomes will include the interim cascade steps:

- S1a. Testing for HCV RNA;
- S1b. Assessment of fibrosis staging;
- S1c. Completion of DAA treatment (receiving the last prescribed medication supply);
- S1d. Testing for HCV RNA at 12 weeks after treatment completion;

Factors that affect treatment effectiveness:

- S2a. DAA treatment motivation (summary score measured by the investigator-developed questionnaire at baseline);
- S2b. DAA treatment adherence (defined as percentage of doses taken using two measures: visual analog scale administered at treatment completion, and pill counts at each dispensing visit);
- S2c. Treatment satisfaction (measured by investigator-developed questionnaire at treatment completion);

Treatment outcomes:

- S3a. Quality of Life (measured by SF-12 questionnaires at all four interviews);
- S3b. Re-infection (measured at 12 months after treatment completion among those achieving SVR).

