### 3.5.6 Data collection

Given the primary and secondary outcomes of interest, data collection for Aim 1 will include three main sources: clinical chart review data and quantitative survey of patients.

**De-identified medical chart review** data extracted by authorized clinic staff will inform outcomes P1-P3, S1a-d and S3b. We will use the electronic Simple Treatment Monitoring Application (STMA)

developed and used in our previous [35] and ongoing projects to collect detailed data on all relevant assessments and treatments, including HCV diagnostic tests, pre-treatment assessments, DAA treatment prescription, on-treatment and post-treatment monitoring, OAT admission and discharge, OAT medication prescription. The database will also collect information on important clinical covariates, including HIV, TB and HBV co-infection, mental health screening and its results, prescription of ART and other medications and side effects. STMA data will be collected on a monthly basis from all sites.

It is expected that physicians at the SHIM sites will comprehensively manage HCV care, and the medical charts and STMA will contain all up-to-date diagnostics and treatment information. However, all SOC sites' patients and possibly some SHIM patients will receive HCV services elsewhere, and their HCV-related clinical data will not be available at the OAT clinic. To ensure completeness of the key outcome data for all participants, we will use an external clinical data verification procedure, similar to one used in our ongoing IMPACT project. In order to avoid intervention contamination, this procedure is conducted by research staff, and not by OAT clinic personnel. At the end of each quarterly clinical data collection cycle, the data manager will generate the HCV treatment cascade report in STMA. For each patient who will not have information about any of the three primary clinical endpoints (HCV diagnosis, treatment initiation, post-treatment HCV RNA PCR) in the report, the interviewers will conduct a brief follow-up by phone. If the patient will report receiving this service, the interviewer will ask about when and where the service was received. At the second stage, the interviewers will contact the respective healthcare facilities to verify the receipt of the services and results (for assessments). This procedure will be enabled by a separate third-party disclosure agreement signed by the patient.

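### Re-infection (S3b) has no reliable, arm-neutral capture route: the 12-month test is optional and unscheduled, and the off-site verification call is never triggered for it

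*Combined protocol and SAP*

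**What the plan says.** - **Endpoint.** Section 3.5.5, S3b: "Re-infection (measured at 12 months after treatment completion among those achieving SVR". The Summary adds a caveat: "Although not sufficiently powered, we will measure re-infection rates among those achieving SVR".
- **Test.** Section 3.2, for participants who complete the SVR PCR: "HCV RNA PCR for re-infection assessment (12 month after treatment completion) will be recommended". The next sentence reads "Cost of re-infection assessment will be reimbursed by the project". No difference by arm is stated.
- **Schedule.** The table in section 3.5.6 has its last column 12 weeks after treatment completion. There is no 12-month column.
- **Data source.** Section 3.5.6 assigns S3b to chart review by OAT clinic staff. It then says that all SOC patients, and possibly some SHIM patients, will get HCV services elsewhere, so their HCV data will not be at the OAT clinic.
- **Verification.** To fill that gap, interviewers telephone each patient who lacks information on any of the "three primary clinical endpoints (HCV diagnosis, treatment initiation, post-treatment HCV RNA PCR"), and then confirm with the facility named.
- **Analysis.** Section 3.5.8 fixes the denominator for the cascade indicators only. It says that secondary outcomes will be tested, with SOC as the reference, and it describes missing-data methods in general terms. It has no rule for SVR achievers without a 12-month test.

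**The concern.** The plan recognises that SOC patients' HCV data sit outside the OAT clinic and builds a procedure to retrieve them. That procedure is keyed to events up to the SVR12 result. S3b begins where those events end, so the one endpoint that depends on a test about nine months after the last scheduled contact is the one that the procedure does not reach.

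What is at stake is a comparison by arm in which SHIM tests are visible on the OAT chart and SOC tests mostly are not. A difference in recorded re-infection could then reflect where the result was filed and not how often patients were re-infected. In one direction this would look like more re-infection under integrated care.

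**Working it through.** The documents state no re-infection rate, test uptake or sample size for S3b, so there is no figure to reproduce. The check is whether the described procedures can capture the endpoint, followed by an illustration with assumed inputs.

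**1. Does the verification trigger reach the 12-month test?** The trigger list in section 3.5.6 is set against what a patient with recorded SVR already has on file:

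| Trigger item | Status in a patient with recorded SVR |
|---|---|
| HCV diagnosis | present (RNA confirmation is needed to stay in the study) |
| Treatment initiation | present (P3 counts from treatment completion) |
| Post-treatment HCV RNA PCR | present (this is the SVR12 result) |
| RNA test at 12 months | not on the list |

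Nothing is missing, so no call is made. S3b applies only to SVR achievers, so this holds for its whole population.

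**2. Is the gap equal across arms?** Section 3.5.6 expects SHIM physicians to manage HCV care and their charts to hold the results. It expects the HCV data of all SOC patients to be elsewhere. Prompting may differ too. Annual RNA testing after treatment is part of the SHIM algorithm (section 3.1.2, step 5), whereas section 3.1.1 describes SOC follow-up RNA tests only as a check of treatment effectiveness.

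**3. Period at risk.** By section 3.1.2, "HCV RNA PCR to confirm SVR will be performed 12 weeks following completion of therapy". Re-infection after SVR can be seen only from then on: 52 − 12 = 40 weeks, and 40/52 = 0.77. This is the same in every arm.

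**4. If untested patients were counted as not re-infected.** Assume a constant incidence of 10 per 100 person-years in every arm.

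- Risk over 40 weeks = 1 − exp(−0.10 × 40/52) = 7.4%.
- Recorded proportion = captured uptake × 7.4%.

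| Assumed captured uptake, SHIM / SOC | Recorded, SHIM / SOC | Ratio (true ratio 1.0) |
|---|---|---|
| 80% / 80% | 5.9% / 5.9% | 1.0 |
| 80% / 50% | 5.9% / 3.7% | 1.6 |
| 90% / 30% | 6.7% / 2.2% | 3.0 |
| 50% / 80% | 3.7% / 5.9% | 0.62 |

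The ratio is simply the ratio of uptakes, so it does not depend on the assumed incidence.

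**5. If only tested patients are analysed.** With uptake u and untested patients at k times the risk of tested ones, the tested-only risk is 7.4% / (u + (1 − u)k). At u = 0.6:

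- k = 0.5: 7.4 / 0.8 = 9.3%, too high.
- k = 1: 7.4%, correct.
- k = 2: 7.4 / 1.4 = 5.3%, too low.

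**6. Calendar time.** Section 3.4.4 says: "Since the study data collection period is 18 months". Suppose this is calendar time covering enrolment and follow-up (an assumption). Then 18 months is about 78 weeks. A 12-week course plus 52 weeks takes 64, which leaves about 14 weeks for enrolment and work-up, and later starters could not reach the test. If the 18 months run per patient, this does not arise.

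**The case against.** A reader might go further and infer that S3b is calculated over all SVR achievers, that it is therefore biased low, and that it is lowest in SOC. The documents do not support that.

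- **Denominator.** Measured among those achieving SVR names the eligible population. It fits a tested-only analysis equally well. The stated missing-data approach (missing-at-random models, with multiple imputation as an example of a sensitivity method) is not one that sets missing to negative.
- **Window.** The 40 weeks are the time frame of any re-infection measure that starts from SVR12. They mislead only if the result is labelled as 12 months at risk.
- **A combined figure.** One could multiply 0.77 by the 83% retention in section 3.5.7 (0.83 × 0.77 = 0.64) and call the rate 36% too low. But 83% is a floor on retention in the team's other studies, not an uptake of this PCR, and the plan never states the rate to which the 0.77 would apply.
- **SOC capture near zero.** Project reimbursement applies without distinction by arm and may leave a record of tests done elsewhere. The third trigger item carries no time limit and could be read to include later tests.
- **Importance.** The Summary concedes low power, and section 3.5.8 does not name re-infection among the secondary outcomes that it lists for modelling.

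All of this stands against the stronger reading. It does not close the gap. Reimbursement is not named as a data source for S3b, and a trigger that fires on missing information is satisfied once the SVR12 result is on file, however broadly the item is read. Low power widens the interval but does not make capture equal between arms.

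**Conclusion.** The point holds as a defect of capture. Followed as written, the plan has no scheduled measurement of S3b, and its recovery procedure for off-site results does not extend to it. Lower captured testing in SOC than in SHIM is the likely consequence. That is an inference from section 3.5.6, not a stated or computed result.

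The size and direction of any bias cannot be derived from the documents. The ratio of 1.6 rests on two assumptions: uptake of 80% against 50%, and untested patients counted as not re-infected. With equal captured uptake it is 1.0. A tested-only analysis removes this artefact only if testing is unrelated to risk.

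The effect is confined to a secondary, largely descriptive endpoint. The primary cascade outcomes are not touched. The change is still worth making, because it is cheap and the imbalance is built into the procedure.

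**What to change.** 1. In section 3.5.6, add an HCV RNA test after SVR12 (12 months after treatment completion) to the telephone and facility verification list, for SVR achievers in all three arms.
2. Add a 12-month data collection point to the schedule table in section 3.5.6, to match sections 3.2 and 3.5.5.
3. In section 3.5.8, state that SVR achievers without a later test are not counted as free of re-infection. Report the number tested out of SVR achievers by arm.
4. Start person-time at the SVR12 test date, or label the result as a risk over about 40 weeks after SVR12.
5. Give bounds for untested patients, for instance by letting their risk range from half to twice that of tested patients. With 60% tested and 7.4% of those positive, this gives 7.4 × (0.6 + 0.4 × 0.5) = 5.9% to 7.4 × (0.6 + 0.4 × 2) = 10.4%.
6. State whether the 18 months in section 3.4.4 are calendar time or per patient, and whether late enrollees will be followed to the 12-month point.

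The cost is protocol and SAP wording, a later contact with SVR achievers, and one more item in an existing call. The test is already reimbursed. The denominator will be smaller and the interval wider, and some bias will remain if the patients who test differ in risk from those who do not.

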### 3.5.6 Data collection

Given the primary and secondary outcomes of interest, data collection for Aim 1 will include three main sources: clinical chart review data and quantitative survey of patients.

**De-identified medical chart review** data extracted by authorized clinic staff will inform outcomes P1-P3, S1a-d and S3b. We will use the electronic Simple Treatment Monitoring Application (STMA)

developed and used in our previous [35] and ongoing projects to collect detailed data on all relevant assessments and treatments, including HCV diagnostic tests, pre-treatment assessments, DAA treatment prescription, on-treatment and post-treatment monitoring, OAT admission and discharge, OAT medication prescription. The database will also collect information on important clinical covariates, including HIV, TB and HBV co-infection, mental health screening and its results, prescription of ART and other medications and side effects. STMA data will be collected on a monthly basis from all sites.

It is expected that physicians at the SHIM sites will comprehensively manage HCV care, and the medical charts and STMA will contain all up-to-date diagnostics and treatment information. However, all SOC sites' patients and possibly some SHIM patients will receive HCV services elsewhere, and their HCV-related clinical data will not be available at the OAT clinic. To ensure completeness of the key outcome data for all participants, we will use an external clinical data verification procedure, similar to one used in our ongoing IMPACT project. In order to avoid intervention contamination, this procedure is conducted by research staff, and not by OAT clinic personnel. At the end of each quarterly clinical data collection cycle, the data manager will generate the HCV treatment cascade report in STMA. For each patient who will not have information about any of the three primary clinical endpoints (HCV diagnosis, treatment initiation, post-treatment HCV RNA PCR) in the report, the interviewers will conduct a brief follow-up by phone. If the patient will report receiving this service, the interviewer will ask about when and where the service was received. At the second stage, the interviewers will contact the respective healthcare facilities to verify the receipt of the services and results (for assessments). This procedure will be enabled by a separate third-party disclosure agreement signed by the patient.

For the secondary outcomes S2b-c, we will collect data using a **paper-based adherence form** administered by clinical personnel during patient visits at treatment initiation, medication pick-up at 4 and 8 weeks, and treatment completion at 12 weeks after initiation. The baseline form will assess self-efficacy and anticipated barriers to treatment adherence for the whole treatment period. The follow-up forms will assess treatment satisfaction, past 30-day and 7-day adherence using visual analog scale [36], side effects, reasons for non-adherence, and reasons for treatment discontinuation (if occurred). At treatment completion, the form will additionally assess the readiness and anticipated barriers to SVR check at 12 weeks after.

For the secondary outcomes S2a and S3a and relevant co-variables, we will collect data using a **patient survey**. The survey will be conducted for the pilot patients and all 3 arms of the main phase at baseline, treatment completion (or 12 weeks after initiation if not completed or 16 weeks after the baseline if not started) and 12 weeks after treatment completion (or 24 weeks after treatment initiation if not completed, or 28 weeks after the baseline if not initiated treatment).

The baseline survey will be administered after confirmation of the diagnosis using HCV RNA test. Patients who will test negative for HCV RNA will be excluded from the following study procedures.

All patient surveys will be collected by an independent interviewer, using study ID via UIPHP REDCap server with clerical checking and patient safeguards described in detail in the human subjects section.

The surveys will include demographics, geospatial assessment, depression (PHQ-9), substance use, alcohol use disorders (AUDIT-C), HIV comorbidity and treatment history, Chronic Liver Disease Questionnaire-Hepatitis C Version (CLDQ-HCV) [37], trust in physician scale [38, 39], HIV risk behaviors, family and social support [40], drug use and mental illness stigma [41], and socio-demographic information.

The baseline survey will additionally assess knowledge about HCV, history of HCV diagnosis and treatment, barriers and facilitators to diagnosis and treatment experienced previously. The post-treatment surveys will assess anticipated and experienced barriers and facilitators to post-treatment monitoring. The forms will be completed by clinical personnel at medication pickup visits, and then transferred to research staff for data entry into REDCap. The forms will contain the study ID and will not contain any personally identifiable information.

The schedule of assessments is presented in the adjacent table.

	Enrollm ent	Tx init.	Tx init. + 4 weeks	Tx init. + 8 weeks	Tx compl.	Tx compl. + 12 weeks
Screening and consent	X					
Diagnosis confirmation and lab testing	X					
Survey	X				X	X
Medication dispensing		X	X	X		
Adherence form		X	X	X	X	
SVR confirmation						X
Qualitative assessment	X					X

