Aim 3's analysis will involve three distinct strategies. First, we will examine the time difference in HCV cascade elements (% diagnosed, % treated, % achieving SVR), with sub-analyses for geographic area and OAT dropout +/- ECHO vs SOC setting. To do this, we will use a generalized mixed linear model (with a logit link), where group will vary by either study arm or by geographical area. Our dependent variables will include: 1) a binary indicator for whether an individual patient achieved the desired HCV diagnosis/treatment coverage cut-off (e.g. diagnosis coverage >80%), as previously used to measure comprehensive and holistic integrated primary care for PWID receiving buprenorphine [42]. The same approach will then be used for secondary individual outcomes (treatment motivation and adherence, treatment satisfaction, quality of life), which we have done previously when integrating addiction treatment into specialty services in the US [43] and Ukraine [12]. 2) treating the primary and secondary indicators as a continuous variables. Any changes in national guidelines that might influence HCV treatment availability would not be scored until after at least 1 year after publication in order to allow for uptake changes by clinicians. Our covariates will include time trends, client-level variables including demographic characteristics, fibrosis stage, treatment motivation and adherence, addiction severity and mental health measures, as well as organizational and provider level measures (from Aim 2).

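### Adherence and satisfaction (S2b-c) have no stated collection route for participants treated away from the OAT clinic, so they are likely to be differentially missing in the SOC referent arm

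*Combined protocol and SAP*

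**What the plan says.** Section 3.5.5 defines S2b by two measures, a "visual analog scale administered at treatment completion, and pill counts at each dispensing visit", and S2c by an investigator-developed questionnaire at treatment completion.

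Section 3.5.6 assigns both outcomes to one instrument, a form on paper that is "administered by clinical personnel during patient visits at treatment initiation", then at the 4- and 8-week pick-ups and at completion in week 12. It adds: "The forms will be completed by clinical personnel at medication pickup visits, and then transferred to research staff for data entry into REDCap". The listed follow-up contents are satisfaction, 7- and 30-day adherence on a visual analog scale (VAS), side effects, and reasons for non-adherence and discontinuation. Pill counts are not listed.

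In the SOC arm, 3.1.1 has the OAT clinics refer patients to hepatology centers for treatment. Section 3.5.6 accepts the consequence: all SOC sites' "patients and possibly some SHIM patients will receive HCV services elsewhere", with their HCV clinical data not held at the OAT clinic.

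Section 3.5.8 nevertheless says of the between-arm model: "The same approach will then be used for secondary individual outcomes (treatment motivation and adherence, treatment satisfaction, quality of life". It names SOC as the referent when it describes the testing of secondary and process measures, and it lists adherence among the model covariates.

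**The concern.** The form is tied to the DAA treatment visits. In the SHIM arms these normally take place at the OAT clinic. A SOC OAT clinic refers its patients out for treatment, so the plan gives it no DAA pick-up visit at which to complete the form. Whether S2b-c are recorded would then depend on where the participant is treated, and that is what the randomization changes.

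At stake are the planned SOC comparisons of adherence and satisfaction, and any Aim 3 model that uses adherence as a covariate. A complete-case fit of such a model would lose SOC starters disproportionately. Missing-at-random models and multiple imputation would have few observed SOC values to draw on. The reassurance about missing data in 3.5.8 concerns clinical source documents and the survey (more than 90% expected at 24 weeks). It says nothing about this form.

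**Working it through.** The plan states no figure on this point, so the check sets sources against outcomes. A short illustration of size follows.

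**Which source could supply S2b-c for a participant treated elsewhere?**

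| Source (3.5.6) | Assigned outcomes | Reaches care given elsewhere? | Supplies S2b-c there? |
|---|---|---|---|
| Chart review / STMA | P1-P3, S1a-d, S3b | Not by itself | No |
| External verification (phone, then facility) | Triggered by missing diagnosis, treatment initiation or post-treatment RNA result | Yes | No; it confirms services and test results |
| Patient survey by independent interviewer | S2a, S3a | Yes; all three arms | No; listed contents include neither DAA adherence nor treatment satisfaction |
| Paper adherence form | S2b-c | No arrangement stated | Only if someone completes it; none named for SOC |

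No section arranges for hepatology-center staff to complete the form, or for OAT staff or interviewers to do so for patients who are dispensed DAA elsewhere. SHIM participants treated elsewhere face the same gap.

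**Pill counts.** They are part of the S2b definition, but they are not among the listed contents of the form or the STMA, nor in the schedule of assessments.

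**Illustration of size.** The inputs are 160 participants per arm, 480 in total (3.5). All initiation and capture rates below are assumptions.

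Overall capture = (320 × c_SHIM + 160 × c_SOC) / 480, as if everyone started DAA:

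- c_SHIM = 100%, c_SOC = 0%: 320/480 = 66.7%
- c_SHIM = 100%, c_SOC = 25%: 360/480 = 75.0%
- c_SHIM = 100%, c_SOC = 50%: 400/480 = 83.3%
- c_SHIM = 90%, c_SOC = 0%: 288/480 = 60.0%

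In the first three cases the whole shortfall lies in the referent arm.

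SOC participants with data = 160 × (share starting DAA) × (share of starters with a form):

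| SOC share starting | Starters | Form in 0% | Form in 25% | Form in 50% |
|---|---|---|---|---|
| 10% | 16 | 0 | 4 | 8 |
| 20% | 32 | 0 | 8 | 16 |
| 40% | 64 | 0 | 16 | 32 |
| 60% | 96 | 0 | 24 | 48 |

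**Separating the form's effect from low initiation.** The detectable standardized difference at 80% power, two-sided 5%, against one SHIM arm with all 160 observed is (1.960 + 0.842) × √(1/n + 1/160). With 64 SOC starters all observed it is 0.41. With 25% captured (n = 16) it is 0.73. The step from 0.41 to 0.73 is due to capture alone. Clustering is ignored and the SHIM arm is taken as complete, so both values are optimistic.

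**The case against.** The strongest reply is that the plan leaves the SOC mechanism unstated, which is not the same as ruling it out. Clinical personnel are not defined as OAT or SHIM staff. Section 3.5.1 has all sites follow common data collection procedures, and 3.1.2 notes that OAT patients attend regularly, so SOC staff could ask the VAS and satisfaction questions at an ordinary OAT visit. The study also interviews hepatology physicians (3.4.2), so those centers are not wholly out of reach.

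Part of this stands: the extent of SOC missingness is inferred, and zero capture is not established. But common procedures at OAT sites do not create a DAA pick-up visit at a clinic that refers its patients out for treatment. Interviewing hepatology physicians is not an arrangement for them to complete forms. Pill counts at dispensing could not be obtained at an OAT visit without the dispensing facility.

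Three further replies also have some force:

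- The sentence naming SOC as referent speaks of pre/post comparisons, which fits on-treatment adherence poorly. The between-arm model is still applied explicitly to adherence and satisfaction.
- The form itself is not reproduced, so a reader may not conclude that it lacks a pill-count field, only that its described contents do not mention one.
- A reader might infer that SHIM answers are inflated because the treating clinic asks the questions. The documents give no size for such a bias, and both SHIM arms use the same method, so SHIM v SHIM+ECHO is not obviously affected. The point here does not rest on it.

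**Conclusion.** The point holds in this form: as written, the plan has no route to S2b-c for SOC participants who start DAA, or for SHIM participants treated elsewhere. These outcomes, and the adherence covariate in 3.5.8, are likely to be differentially missing in the referent arm.

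The size cannot be fixed from the documents. Under assumed SOC initiation of 10-60% and capture of 0-50%, between 0 and 48 of 160 SOC participants would contribute.

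A reader might go further and infer that S2b-c will be absent in SOC and the comparison not estimable. That would need zero capture, which the documents do not establish. If few SOC participants start DAA, the referent group is thin whatever instrument is used, and that part is not due to the form.

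Nor are the primary endpoints compromised. P1-P3 come from chart review with external verification, and the primary model in 3.5.8 names region, age, gender and predictors of missingness as its adjustments, not adherence. This is a correction that should be made to two secondary outcomes and one covariate.

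**What to change.** 1. In 3.5.6, add the adherence VAS and satisfaction items to the interviewer-administered survey at treatment completion, for participants who started DAA, in all three arms. Name it as the source for the between-arm comparison of S2b-c. This matches the timing in 3.5.5, and the survey already has fallback timing for those who start but do not complete.
2. Keep the clinic form and pill counts as process data for SHIM participants treated on site. State where pill counts are recorded, and limit pill-count comparisons to SHIM v SHIM+ECHO.
3. In 3.5.8, take the adherence covariate from the same survey source, and report by arm how many DAA starters have a value.
4. Record the actual interval between last dose and interview.

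The cost is a few added survey items and wording changes in 3.5.5, 3.5.6 and 3.5.8. The downside is that the comparison rests on one recall at completion instead of repeated reports. In SOC that recall may come late relative to the 7- and 30-day windows, because initiation elsewhere is learned through quarterly reports and phone follow-up. Item 4 makes any such delay visible.
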